6. EFFICACY ANALYSES

6.1. Primary Efficacy Endpoint

6.1.1. Definition of the Primary Efficacy Endpoint

The primary endpoint of the study is the proportion of COVID-19–related hospitalization or all-cause death by Day 29. The endpoint will be derived by combining the available all-cause death and COVID-19–related hospitalization reported by the site.

COVID-19–related hospitalization is defined as \geq 24 hours of acute care for a reason related to COVID-19, in a hospital or similar acute care facility, including emergency rooms or temporary facilities instituted to address medical needs of those with COVID-19. This includes specialized acute medical care units within an assisted living facility or nursing home. This does not include hospitalization for the purposes of public health and/or clinical study execution. The date and duration of hospital admission, and primary reason for hospitalization (including if the hospitalization is related to COVID-19) will be recorded.

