6.2. Secondary Endpoints

Key Secondary Efficacy Endpoints

The alpha-controlled secondary endpoints include the following:

- Proportion of participants with all-cause hospitalization by Day 29
- Proportion of participants with COVID-19–related MAVs or all-cause death by Day 29
- Proportion of participants with COVID-19-related MAVs by Day 29
- Proportion of participants with all-cause death by Day 29

Medically attended visits are defined as any interactions with health care professionals other than study staff or designees including hospitalization; in-person emergency, urgent, or primary care visits; or any other in-person visit attended by the participant and a health care professional.

Other Secondary Efficacy Endpoints

- Time to COVID-19 symptom alleviation by Day 15
- Change from baseline (Day 1) in SARS-CoV-2 nasal swab viral load at Day 5

Symptom alleviation is defined as all targeted symptoms measured via the SIC questionnaire (Appendix 2) with a rating of 0, or at least 3 points decrease in rating from baseline, or an answer "No" to the question for at least 48 consecutive hours. A new version of the questionnaire that measures COVID-19 symptoms, COVID-19 Symptom Questionnaire, was introduced in protocol Amendment 1 but was not available to any participant by the time of stop of enrollment. Data for the COVID-19 Symptom Questionnaire were not collected.

Targeted symptoms are those listed below:

- Nasal congestion (stuffy nose)
- Runny nose
- Sore throat

- Shortness of breath (difficulty breathing)
- Cough
- Feeling generally unwell (run down)
- Fatigue (tiredness)
- Physical weakness
- Feeling faint
- Muscle aches/pains
- Joint aches/pains
- Headache
- Chills
- Uncontrollable body shaking/shivering
- Fever

The first day of the 48 consecutive hours will be considered the symptom alleviation date. The date and time stamps at which participants complete the questionnaire each day are captured in electronic diary as "Form Saved Time" and will be used to determine whether the requirement of 48 continuous hours is satisfied.

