Proportion of participants with negative SARS-CoV-2 nasal swab viral load at Days 3, 5, 10, and 15	Participants in the Virology analysis set who had SARS-CoV-2 nasal swab collected and nonmissing result of viral load reported at selected visits	Number of participants with negative SARS-CoV-2 nasal swab viral load
Proportion of participants with negative SARS-CoV-2 infectious viral titer at Days 3, 5, 10, and 15	Participants in the Virology analysis set who had SARS-CoV-2 nasal swab collected and nonmissing result of SARS-CoV-2 infectious viral titer reported at selected visits	Number of participants with negative SARS-CoV-2 infectious viral titer

4) Definition of Hospitalization

MAVs type of Emergency Room, non-ICU Hospitalization, ICU Hospitalization, and Hospitalization (unknown ward) could meet criteria for hospitalization if one of the following conditions is met:

- If the duration of the MAV is greater than 24 hours.
- If the duration is missing and end date of the MAV is 1 day after the start date.

Time to hospitalization is calculated as Start date of Hospitalization – First dose date + 1.

5) SARS-CoV-2 positive at baseline

SARS-CoV-2 positive at baseline is defined as test result from central lab.

- Cepheid's Xpert Xpress CoV-2/Flu/RSV plus (Multiplex) test result is positive for SARS-CoV-2 or
- SARS-CoV-2 RT-qPCR test result is numerical viral load result or "<2228cp/mL SARSCoV2 detected", regardless the sample was collected with less than specified volume of test solution.

GS-US-611-6273-Final Analysis-SAP-v1.0

ELECTRONIC SIGNATURES

Signed by	Meaning of Signature	Server Date (dd-MMM- yyyy hh:mm:ss)
PPD	Biostatistics eSigned	24-Jan-2024 01:01:34
PPD	Global Development Lead (GDL) eSigned	24-Jan-2024 17:55:34

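### The hospitalization derivation tests 24 hours on a single medically attended visit and has no rule to link the visits of one continuous stay, so a stay entered as several short visits would not count

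*SAP*

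**What the plan says.** SAP section 6.1.1 defines a COVID-19-related hospitalization as at least "24 hours of acute care for a reason related to COVID-19, in a hospital or similar acute care facility, including emergency rooms or temporary facilities". Protocol section 8.5.1 has the same definition. Protocol section 8.5.2 uses it without the COVID-19 reason for all-cause hospitalization. In each case the threshold applies to a period of acute care, not to time in one location.

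SAP Appendix 3, item 4 turns this into a derivation. It lists four location-specific types: "MAVs type of Emergency Room, non-ICU Hospitalization, ICU Hospitalization, and Hospitalization (unknown ward) could meet criteria for hospitalization". One of two conditions must then hold: "If the duration of the MAV is greater than 24 hours", or, as a fallback, "If the duration is missing and end date of the MAV is 1 day after the start date". On timing it says "Time to hospitalization is calculated as Start date of Hospitalization", minus the first dose date, plus 1.

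SAP section 6.2 gives the unit being tested: "Medically attended visits are defined as any interactions with health care professionals other than study staff or designees including hospitalization". Neither document says whether a transfer within a hospital continues the same MAV or opens a new one. Neither tells the programmer to join MAVs, add their durations, or carry the start date back to the first of them.

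**The concern.** The definition and the programmed rule have different units. The definition counts total hours of acute care and expressly includes the emergency room. The rule looks at one MAV of one location type at a time. If a stay that passes from the emergency room to a ward and then to intensive care is entered as three MAVs, each is tested alone, and a stay well over 24 hours can fail on every one. If only a later part passes, the event is dated from that part and not from arrival.

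The derivation feeds the primary endpoint and all-cause hospitalization, the first key secondary endpoint in the testing sequence. SAP section 2.3 says enrollment stopped at less than half the planned number because primary events were fewer than expected, so there are few events to lose. SAP sections 3.3 and 6.1.3 also drop a stratification factor from the model when a stratum has 5 events or fewer. A lost event could therefore change the model as well as the count.

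**Working it through.** **1. The rule applied to example stays.** Each stay below is continuous, is split by location, and has all durations recorded. The rule is that an MAV qualifies if its own duration exceeds 24 hours, and the event date is the start date of the qualifying MAV. The stays are illustrations, not trial data.

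| Stay | Total | Longest part | Counted? | Date |
|---|---|---|---|---|
| Emergency room 10 h, ward 16 h | 26 h | 16 h | No | none |
| Emergency room 8 h, ward 20 h, ICU 22 h | 50 h | 22 h | No | none |
| Emergency room 14 h from 20:00, ward 48 h | 62 h | 48 h | Yes | 1 day late |
| Emergency room 20 h from 10:00, ward 22 h, ICU 72 h | 114 h | 72 h | Yes | 2 days late |

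All four stays meet the section 6.1.1 duration from the first MAV. The first two are lost. In the third, the ward starts at 10:00 the next day. In the fourth, the ICU starts 42 h after 10:00, at 04:00 on the third calendar day. A transfer on the same calendar date causes no shift, because time is counted in dates.

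**2. How many events there are to lose.** Inputs are 2300 participants randomized 1:1, a placebo rate of 2%, a ratio of 0.25 and two-sided alpha of 0.05 (SAP sections 1.2 and 1.3).

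- Planned events: 1150 × 0.02 + 1150 × 0.005 = 23 + 5.75 = 28.75.
- The plan's own power, by two proportions with p̄ = 0.0125: the null SE is √(2 × 0.0125 × 0.9875 / 1150) = 0.004633, and the alternative SE is √((0.02 × 0.98 + 0.005 × 0.995) / 1150) = 0.004623. Power = Φ[(0.015 − 1.96 × 0.004633) / 0.004623] = Φ(1.280) = 90.0%.
- Freedman's formula: Φ(√28.75 × 0.75/1.25 − 1.96) = 89.6%. Both reproduce the SAP's figure of approximately 90%. Schoenfeld's formula gives 96.1%, in line with the protocol's claim of more than 90%.
- After the early stop: fewer than 50% of 2300 means at most 1149 participants. Expected events at the design rates are 1149/2 × (0.02 + 0.005) = 14.4, and fewer if rates were lower, as SAP section 2.3 reports.
- The weight of any single event is then 1/14.4 = 7%.

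**3. What a given loss would cost.** The documents do not give the share of stays affected. As an assumption, suppose the same share of events is lost in both arms of the planned 2300-participant trial:

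| Share lost | Events | Power (two proportions) |
|---|---|---|
| 0% | 28.75 | 90.0% |
| 5% | 27.3 | 88.4% |
| 10% | 25.9 | 86.7% |
| 20% | 23.0 | 82.5% |
| 30% | 20.1 | 77.2% |

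These rows show sensitivity only. They do not estimate how often the problem occurs.

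**The case against.** The strongest reply is that the problem depends on a form nobody can see here. Item 4 tests an MAV, and it does not say that a transfer opens a new one. Section 6.1.1 says sites record "The date and duration of hospital admission, and primary reason for hospitalization", which fits one entry per admission, and the MAV definition names hospitalization itself as an interaction. If one stay is one MAV, nothing is lost. This stands, and it makes the point conditional. The separate emergency-room, non-ICU and ICU types suggest entry by location but do not prove it.

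There are also partial safeguards:
- Item 4 says only that these types could qualify, and section 6.1.1 works from site-reported hospitalizations, so manual review is possible.
- In-patient hospitalization is a seriousness criterion (protocol 7.1.2), and SAEs are reconciled with the safety database (SAP 7.1.4).
- When duration is missing, the date fallback can rescue a part that ends the next day.
- A participant who dies by Day 29 still counts in the primary endpoint through death.

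These limit the loss, but none is a rule for linking MAVs.

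A reader might infer three stronger things that the documents do not support. The first is that sites or countries split stays differently; nothing describes how any site completes the form. The second is that the comparison is biased. The trial is double-blind, nothing shows that recording depends on arm, and equal proportional loss lowers precision without moving the ratio. The third is that 7% is the size of the defect. It is the weight of any one event out of 14.4.

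**Conclusion.** The point holds in conditional form. As written, item 4 does not carry out the section 6.1.1 definition for a stay entered as more than one MAV. A continuous stay whose parts are each 24 hours or less is left out of both the primary endpoint and all-cause hospitalization. Whether any stay was entered that way is an assumption, and the frequency is unknown.

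Lost events are what matter, because about 14 or fewer would be expected at the design rates. Dating a stay 1 to 2 days late has little effect on a Cox model unless it crosses Day 29 or changes the order of events. No bias between arms is shown, and the point does not invalidate the primary comparison. It is still more than missing detail, because following the stated rule can give a wrong endpoint status. Whether the limit should be more than 24 hours or at least 24 hours is a separate question.

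**What to change.** Add a linking step to Appendix 3, item 4, before the 24-hour test:

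- Join MAVs of the four types that form one uninterrupted stay. The next start is at or before the previous end by date and time, or a direct transfer is recorded. Allow a short stated gap, so that a transfer across midnight is not split. Do not join after a discharge home, even if the participant returns the same day.
- Apply the 24-hour test to the span from the first start to the last end, using dates where times are missing.
- Date the event at the first start.
- For the primary endpoint, require the joined stay to be for a COVID-19-related reason, so that unrelated hours do not lift it over the limit.

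If the eCRF already enforces one record per admission with emergency-room time included, the step changes nothing, and the SAP or CSR should say so.

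The cost is a programming rule on data already collected, plus a choice of gap length and a check of the few stays affected. No new data are needed. SAP section 1 provides for changes after finalization to be documented in the CSR.

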# 8.5.2. Secondary Analyses

The secondary endpoints of COVID-19–related MAVs or all-cause death by Day 29 and all-cause death will be analyzed similarly as in the primary analysis. The secondary endpoints of all-cause hospitalization by Day 29 and COVID-19–related MAVs will be analyzed using a competing risk analysis approach, with death as the competing risk.

Medically attended visits are defined as any interactions with health care professionals other than study staff or designees including hospitalization; in-person emergency, urgent, or primary care visits; or any other in-person visit attended by the participant and a health care professional. The nature and cause of the visit should be identified.

All-cause hospitalization is defined as  $\geq 24$  hours of acute care, in a hospital or similar acute care facility, including emergency rooms or temporary facilities instituted to address medical needs of those with COVID-19. This includes specialized acute medical care units within an assisted living facility or nursing home. This does not include hospitalization for the purposes of public health and/or clinical study execution. The date and duration of hospital admission, and primary reason for hospitalization (including if the hospitalization is related to COVID-19) will be recorded.

A gatekeeping approach will be used for testing the key secondary endpoints. The endpoints will be tested in the following sequential order:

- Proportion of participants with all-cause hospitalization by Day 29.
- Proportion of participants with COVID-19-related MAVs or all-cause death by Day 29.
- Proportion of participants with COVID-19-related MAVs by Day 29.

Change from baseline in SARS-CoV-2 nasal swab viral load to Day 5 will be summarized by treatment groups and compared between treatment groups using a mixed-effects model repeated measures (MMRM) approach.

The Kaplan-Meier product limit method will be used to estimate, and log-rank test will be used to compare treatment groups for the time to symptom alleviation of targeted COVID-19 symptoms.

Handling of intercurrent events for key secondary efficacy endpoints is defined in Section 8.5.3.

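### The SAP's programming rule for hospitalization uses a strict 24-hour cut-off where the protocol and SAP definition is inclusive, and its missing-duration condition is ambiguous for stays of two or more days

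*SAP*

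**What the plan says.** **Definition.** SAP 6.1.1 and protocol 8.5.1 define COVID-19-related hospitalization with a greater-than-or-equal sign placed directly before "24 hours of acute care for a reason related to COVID-19, in a hospital or similar acute care facility". Protocol 8.5.2 uses the same inclusive 24-hour threshold for all-cause hospitalization: "hours of acute care, in a hospital or similar acute care facility, including emergency rooms". SAP 6.1.1 takes the COVID-19-related component of the primary endpoint from "hospitalization reported by the site". It also says that the following will be recorded: "The date and duration of hospital admission, and primary reason for hospitalization".

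**Programming rule.** SAP Appendix 3, item 4, says that emergency-room and hospital visit types "could meet criteria for hospitalization if one of the following conditions is met". The two conditions are:

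1. "If the duration of the MAV is greater than 24 hours"
2. "If the duration is missing and end date of the MAV is 1 day after the start date"

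There is no third condition. SAP 6.5, which lists changes from the protocol's efficacy analyses, does not mention the hospitalization threshold.

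**The concern.** An event definition and the code specification that implements it should select the same events. Here they differ at the boundary and possibly beyond it, with no stated reason. Strict inequality is not a convention of the appendix: example 6 of its symptom-alleviation examples counts an interval from 8:00 on Day 3 to 8:00 on Day 4 as satisfying a 24-hour requirement.

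The exposure differs by endpoint:

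- **All-cause hospitalization** is clearly exposed. It is first in the testing order of the key secondary endpoints. SAP 6.2 does not define it, so item 4 is its only derivation in the SAP; the inclusive definition stands in the protocol.
- **The hospitalization part of the primary endpoint** is possibly exposed. SAP 6.1.1 bases it on site reports, and the SAP does not say how item 4 relates to them.
- **Time to symptom alleviation** is possibly exposed. Hospitalization for COVID-19 is a composite intercurrent event there, with censoring at Day 14 (SAP Table 6-1 and Appendix 3, item 1). The SAP does not say whether item 4 defines that hospitalization.
- **The visit-based and death endpoints** are not exposed. SAP 6.2 counts hospitalization as a visit with no minimum duration: "Medically attended visits are defined as any interactions with health care professionals other than study staff or designees including hospitalization".

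**Working it through.** The documents give no figure for this point, so the check is a comparison of the two rules case by case.

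**Inputs.** Definition: duration ≥ 24 h (protocol 8.5.1 and 8.5.2; SAP 6.1.1). Rule, read literally: duration > 24 h, or duration missing and end date minus start date equal to 1 day (SAP Appendix 3, item 4).

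**Bounds when only dates are known.** If the end date is d calendar days after the start date (d ≥ 1), the stay is longer than 24 × (d − 1) hours and shorter than 24 × (d + 1) hours. For d = 1 that is more than 0 h and less than 48 h. For d = 2 it is more than 24 h.

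| Case | Item 4, literal | Definition |
|---|---|---|
| Duration 23.9 h | no | no |
| Duration 24.0 h | **no** | **yes** |
| Duration 24.1 h | yes | yes |
| Duration missing, same-day end | no | no |
| Duration missing, d = 1 | yes | undetermined (0 to 48 h) |
| Duration missing, d = 2 | **no** | **yes** (more than 24 h) |
| Duration missing, d = 3 | **no** | **yes** (more than 48 h) |
| Duration missing, d = 10 | **no** | **yes** (more than 216 h) |

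**Reading the table.** The mismatch at 24.0 h follows directly from the wording. The mismatches at d = 2 and beyond hold only if duration is a separate recorded field that can be blank while both dates are present. If duration is computed from the dates, those stays already satisfy condition 1, and condition 2 settles only the undetermined next-day case.

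**Can the effect be turned into a probability?** SAP 2.3 says that enrollment stopped below 50% of plan (0.5 × 2300 = 1150) because primary events were fewer than expected, so one stay might seem decisive. Take hypothetical event counts a and b in two arms of equal size and remove one event from the larger count. Two approximations are available:

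- log-rank: z = |a − b| / √(a + b)
- Wald, Cox-type: z = |ln(a/b)| / √(1/a + 1/b)

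| Counts | Log-rank p | Wald p |
|---|---|---|
| 1 vs 7 | 6/√8 = 2.12; 0.034 | 1.946/1.069 = 1.82; 0.069 |
| 1 vs 6 | 5/√7 = 1.89; 0.059 | 1.792/1.080 = 1.66; 0.097 |
| 3 vs 11 | 8/√14 = 2.14; 0.033 | 1.299/0.651 = 1.99; 0.046 |
| 3 vs 10 | 7/√13 = 1.94; 0.052 | 1.204/0.658 = 1.83; 0.067 |

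Losing one event from 3 vs 11 crosses 0.05 on both approximations. Losing one from 1 vs 7 crosses on the log-rank only. SAP 6.1.3 reports a Cox p-value and, in addition, a stratified log-rank p-value. The answer therefore depends on the test and on assumed counts. It also presumes that a stay is misclassified, and the documents give no chance of that. All these counts concern the primary endpoint, which is only possibly exposed; no expected rate is given for all-cause hospitalization.

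**The case against.** The strongest reply is that condition 2 is coherent as it stands. With clock times missing, dates alone settle every case except a next-day end, and that is exactly the case condition 2 names. Longer stays would pass condition 1 on dates alone. The visit-collection text (protocol 6.3.2.7 and the MAV footnote to protocol Table 1) names no separate duration field. This stands as a plausible reading. Against it, SAP 6.1.1 says that duration is recorded, and item 4 does not say that it is derived. A reader might infer that the rule certainly drops multi-day stays. The documents do not support that; they leave the question open.

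A second reply is that item 4 is only a screen, since a visit that passes merely could qualify, and that the site report decides. That may be so for the primary endpoint. A reader might infer that item 4 governs the primary endpoint outright, but SAP 6.1.1 bases it on site reports and no passage gives item 4 precedence. The reply does not remove the boundary mismatch: a screen that rejects a 24-hour stay still rejects a qualifying one.

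A third reply is that data queries are resolved before the final analysis (SAP 2.2) and serious adverse events are reconciled (SAP 7.1.4). These steps may reduce missing durations. No passage links them to this derivation, and they cannot correct an inequality.

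**Conclusion.** One contradiction is certain: a stay of exactly 24 hours meets the definition in the protocol and SAP body and fails the programming rule, and SAP 6.5 does not declare the difference. On its own it affects only durations recorded as exactly 24 hours, which is likely to be few unless durations are rounded to whole hours or days; the documents do not give the recording unit. The multi-day gap is an ambiguity to close and not a demonstrated loss of events.

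The number of affected stays is unknown and may be zero. A reader might infer that one missed stay is likely to overturn the trial result. The documents do not support that: the chance that any stay is misclassified cannot be derived, and the effect of one lost event changes with the test used. All-cause hospitalization, the clearly exposed endpoint, is also tested formally only if the primary endpoint is met (SAP 3.5). Severity: minor.

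**What to change.** In SAP Appendix 3, item 4:

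- Condition 1: duration ≥ 24 hours.
- Condition 2: duration missing and end date one or more calendar days after the start date.

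If a departure from the inclusive threshold is intended, keep the rule and list it with a reason in SAP 6.5.

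This does not decide whether item 4 or the site report governs the primary endpoint, and the edit should not be taken to settle that.

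**Cost.** Two edited lines, with no new data and no new analysis. SAP version 1.0 is already signed, so the change needs a SAP revision or, under SAP Section 1, documentation in the CSR. Either way its timing relative to unblinding should be recorded, because it alters an event rule. One weakness remains: a short stay that crosses midnight and has no recorded duration would still count.
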